**Impact of Changing Cannulation Strategies on Neurologic Injury in Infants with
Respiratory Failure: HUM00236110**

PI: [name]

Document Date: September 19, 2023

Aims and Approach:

From 2019-2021, there was increased use of venoarterial (VA) extracorporeal membrane oxygenation (ECMO) for infants with respiratory failure, up to 92% of neonatal respiratory support in 2021. Our primary aim is to estimate the average effect on the rate of neurologic injury of VA ECMO versus venovenous (VV) among infants with respiratory failure over the period 2013-2018, during which clinicians could choose either cannulation strategy. We will estimate this causal effect using an inverse propensity weighted (IPW) approach. Secondly, we will project this estimated treatment effect forward into the period 2019-2021. The beginning of this period roughly corresponds to start of increased use of VA ECMO. Under the assumption of a homogenous treatment effect across both study periods, we will estimate the rate of neurologic injury that *would have* occurred in 2019-2021, had the rate of VA ECMO *not* increased relative to pre-2019 levels. We hypothesize that our results will point to an increased rate of neurologic injury starting in 2019 due to the increased use of VA ECMO.

Outcome:

The outcome will be the composite occurrence of neurologic injury (ischemic stroke, intracranial hemorrhage, and brain death) that arises during critical illness supported by ECLS as reported to the Extracorporeal Life Support Organization (ELSO) registry, coded as a 0/1 variable (0 = no occurrence was reported during or after ECMO; 1 = one or more occurrence was reported).

Exposure:

The exposure / treatment of interest is the initial cannulation mode used, coded as a 0/1 variable (0= VV dual-lumen or two-site; 1= VA peripheral cannulation only).

Study Population:

We will analyze data from the ELSO registry. All runs satisfying the following inclusion and exclusion criteria will be included in our study population:

Inclusion criteria:

- Patient weighed less than or equal to 10kg at start of ECMO
- Pulmonary support was the indication for ECLS
- Initial cannulation strategy was VV or VA
- The run occurred during the period 2013-2023

Exclusion criteria:

- Patient had CDH
- Patient was post-cardiotomy
- Non-conventional initial cannulation strategies were employed, such as
 - Central Cannulation (surrogate for inability to achieve peripheral cannulation)
 - Veno-veno-arterial ECMO

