 - Initial cannulation approach reported as “other”
- Patient was transported into or out of ELSO center on ECMO support
- Patient had pre-ECLS Cardiac Arrest
- Patient did not have subsequent ECMO runs in the ELSO registry

In addition, to the above criteria, all otherwise-eligible runs from centers that do not have at least one eligible run from each exposure group during the study period will be excluded.

Statistical Analysis Plan:

Step 1 will estimate the probability of being in the exposure group during a period when clinicians could choose either VV or VA ECMO. Among the subsample of patients from the period 2013 to 2018, we will fit a logistic regression model using pre-cannulation center and patient factors to predict the probability of a patient receiving VA ECMO.

We will include in this model factors that precede the start of ECMO and are posited to be associated with both the choice of cannulation strategy as well as the risk of neurologic injury.

We will include the following predictors in the propensity score model:

Unit Type- multinomial categorical

Admitted at birth -binary

Age at cannulation (days)- continuous

Gestational age (semi-continuous to 38 weeks, term infants will older infants will be classified together)

Transfer into the ECMO center- binary

Weight (cont)

Sex- binary

Intubation to Time On (continuous)

Pre-ECLS pH (continuous)

Pre-ECLS pCO₂ (continuous)

Pre-ECLS PO₂ (continuous)

Pre-ECLS HCO₃ (continuous)

Pre-ECLS FiO₂ (continuous)

Pre-ECLS Mean Airway Pressure- oscillator (continuous)

Pre-ECLS Mean Airway Pressure- conventional (continuous)

Pre-ECLS Mean Arterial Pressure (continuous)

Pre-ECLS Pulse Pressure (continuous)

Pre-ECLS Renal Replacement Therapy- binary

iNO- binary

Inhaled epoprostenol- binary

Therapeutic Hypothermia- binary

Vasoactive Infusions- binary

Diagnoses

Meconium Aspiration Syndrome- binary

HIE- binary

Pulmonary hypoplasia- binary

Respiratory Distress Syndrome- binary

Persistent Pulmonary Hypertension- binary

Pulmonary Hypertension- binary

Sepsis- binary

Asthma- binary

Bronchiolitis- binary

Pneumonia - binary

Pertussis- binary

PDA- binary

We will also take into account each center's typical proclivity for VV versus VA ECMO, using either a mixed-effects modeling strategy or the surrogate indicator approach of Li, Zaslavsky, and Landrum (2007)

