In **Step 2**, we will estimate the average treatment effect (ATE) of VA-ECMO in the period 2013-2018 using an IPW approach. We will estimate the ATE using an appropriate estimator that takes into account the clustered nature of the data (runs clustered within ELSO center).

Because the availability of VV ECMO cannulas appropriate for infants changed in 2019, we expect that at this point and afterward clinicians generally chose VA ECMO support more often than they otherwise would have. Using the propensity score model developed in Step 1, we will calculate propensity scores for patients cannulated during 2019-2021, estimating the propensity that a given patient would have received VA ECMO had they received ECLS support in 2013-2018. Using these estimated propensities, in **Step 3**, we will project this estimated ATE from the 2013-2018 cohort into the 2019-2021 cohort, thereby estimating what the rate of neurologic injuries would have been had the availability of VV ECMO cannulas not changed (and assuming a homogenous treatment effect of VA ECMO across periods). If there is a large enough sample size, we will perform a sensitivity analysis in a cohort from 2022-2023, during which there was increased availability of VV-ECMO cannulas and increasing use of VV-ECMO support.

Missingness in the predictors

We anticipate that there will be sporadic missingness in the predictors used to construct the propensity scores. We will use the approach recommended in Leyrat, et al. (2019) to incorporate the partial information available from observations with missingness. Specifically, we will create multiply imputed versions of the data, estimate a separate ATE for each of these completed datasets, and then combine the estimated ATEs across imputations to obtain a single estimated ATE.

References

Leyrat, C., et al. (2019). "Propensity score analysis with partially observed covariates: How should multiple imputation be used?" Stat Methods Med Res **28**(1): 3-19.
Li, F., et al. (2007). Propensity score analysis with hierarchical data. Proceedings of the American Statistical Association Joint Statistical Meetings.

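### Step 3 presents average 2013-2018 practice as practice without the cannula change, so any unmodelled pre-2019 trend in VA use would be credited to, or taken from, that change

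*SAP*

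**What the plan says.** - **Step 1** (SAP, Statistical Analysis Plan): "Among the subsample of patients from the period 2013 to 2018, we will fit a logistic regression model". The predictor list, introduced by "We will include the following predictors in the propensity score model", covers unit type, patient characteristics, pre-ECLS physiology and support, and diagnoses. It has no calendar-time term.
- **Center term:** "We will also take into account each center's typical proclivity for VV versus VA ECMO". Nothing says that this preference may vary over time.
- **Step 3:** patients cannulated in 2019-2021 are scored with that model, "estimating the propensity that a given patient would have received VA ECMO had they received ECLS support in 2013-2018". The projected figure is then described as "what the rate of neurologic injuries would have been had the availability of VV ECMO cannulas not changed".
- **Aims and Approach:** the same quantity is described as the injury rate "had the rate of VA ECMO *not* increased relative to pre-2019 levels".
- **Assumption:** the only one stated for the projection, in both places, is that the VA treatment effect is the same in the two periods.

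**The concern.** Step 3 treats two different counterfactuals as one. The first is what these patients would have received under average 2013-2018 practice, centred on about 2015.5. The second is what they would have received in 2019-2021, centred on 2020, had cannula supply not changed. If use of VA was already drifting within centers, for reasons that the listed covariates do not capture, the two differ. The drift is then added to the excess ascribed to the cannula change, or subtracted from it if VA use was falling.

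This is separate from confounding of the Step 2 ATE. The excess would be misattributed even with an exactly correct ATE and no time trend in injury risk. The homogeneous-effect assumption does not help, because it concerns injury risk by mode and not how the mode was chosen.

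At stake is whether the Step 3 number can be read as injury due to the cannula change.

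**Working it through.** The SAP gives no projected excess to reproduce, so the check is on structure, followed by size under stated assumptions.

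**1. Gap between benchmark and target.** The mid-point of 2013-2018 is 2015.5, that of 2017-2018 is 2017.5 and that of 2019-2021 is 2020. So 2017-2018 lies 2.0 years, and the target period 4.5 years, after the centre of the baseline.

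**2. Formula.** Taking the ATE as a risk difference that is constant across periods:

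excess = ATE × (observed VA share − benchmark share)

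Under a linear drift of d points per year, the benchmark share is the baseline average + d × k. Here k = 0 for the plan, 2.0 for 2017-2018 practice and 4.5 for the extrapolated trend.

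**3. Inputs, all assumed.** ATE 5 points; VA share 65% on average in 2013-2018 and 85% in 2019-2021; d from −2 to +2. The only share in the SAP is up to 92% in 2021, for neonatal respiratory support.

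**4. Results.** The plan gives 5 × (85 − 65)/100 = 1.00 point whatever the drift. As an example of the other columns, d = +2 and k = 2.0 give 5 × (85 − 69)/100 = 0.80.

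| Drift (points/year) | Against 2017-2018 | Against extrapolated trend | Plan's 1.00 is |
|---|---|---|---|
| +2 | 0.80 | 0.55 | 25% to 82% too high |
| +1 | 0.90 | 0.775 | 11% to 29% too high |
| 0 | 1.00 | 1.00 | correct |
| −1 | 1.10 | 1.225 | 9% to 18% too low |
| −2 | 1.20 | 1.45 | 17% to 31% too low |

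In absolute terms, the largest shift in the table is 0.45 points, or 4.5 injuries per 1000 runs (4.5 years × 2 points × 5%).

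**5. Simulation of the mechanism** (200,000 runs per scenario, one covariate, no center effects). Model A was fitted on 2013-2018 without a year term, as planned; model B had a linear year term. Both were projected to 2019-2021. The entries are excess VA share in points.

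| Scenario | Model A | Model B |
|---|---|---|
| Log-odds trend 0.05 per year, no 2019 change | 5.1 | −0.2 |
| Trend 0.10, no 2019 change | 9.9 | 0.4 |
| Trend 0.15, no 2019 change | 13.9 | −0.2 |
| No trend, 2019 jump of 1.0 in log-odds | 19.6 | 19.7 |
| Trend 0.10 plus the same jump | 26.1 | 16.1 |
| Trend only through the modelled covariate, no 2019 change | 0.0 | −0.2 |

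The planned benchmark turns an unmodelled trend into an apparent effect of 2019. It is correct when there is no trend, or when the trend runs through a modelled covariate.

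**The case against.** **The Aims define a benchmark that the plan meets.** The target there is the injury rate had VA use not "increased relative to pre-2019 levels", and the hypothesis concerns increased use of VA rather than cannula supply. For that contrast, pooled 2013-2018 practice is a legitimate reference and earlier drift is part of the increase being measured. This stands. A reader might infer that the second aim as a whole is invalid; the documents do not support that. The difficulty is Step 3's description of the result in terms of cannula availability.

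**Much of any trend is already handled.** The model holds more than 30 patient and unit factors plus center preference, so shifts in case mix or center mix carry into the 2019-2021 propensities. This also stands, and it is why the point is limited to trends that those terms do not explain.

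**A 2022-2023 sensitivity analysis is planned.** A return of VA use towards the predicted level once cannulas were available again would bear partly on drift versus supply. But that analysis depends on sample size, looks forward, and cannot show a pre-2019 trend.

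**No other benchmark is clearly right.** Practice in 2017-2018 removes only 2.0 of the 4.5 years of drift. Because the SAP dates the rise in VA use to 2019 only approximately, those years are also the most exposed to an early rise. Extrapolating a trend is itself an assumption. This stands, and is a reason to use both as sensitivity analyses and leave the primary benchmark as it is.

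**Conclusion.** The point holds in a limited form. Step 3's description in terms of cannula availability needs an assumption that the SAP neither states nor checks: that VA use, given the modelled covariates and center mix, was flat before 2019 and would have stayed so.

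A reader might go further and infer that a trend existed, or that the planned excess is biased upward. The documents show neither. They give no yearly 2013-2018 shares, a falling trend would bias the other way, and with no trend the error is zero.

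With a drift of 2 points per year in either direction, the planned figure would be between 31% too low and 82% too high. Those percentages rest on the assumed ATE, shares and linear drift, and serve only as illustration. This is a cheap improvement to a secondary aim and leaves the primary estimate untouched.

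**What to change.** 1. Keep the 2013-2018 average as the primary benchmark in Step 3, and describe that result as a contrast with average 2013-2018 practice.
2. Show the covariate-adjusted VA share by year for 2013-2018.
3. Add two sensitivity benchmarks: the excess against 2017-2018 practice, and against the extrapolated pre-2019 trend. The latter needs a year term in the Step 1 model and a stated prediction year; a year term alone does not settle which practice is being projected.
4. Run a placebo projection, fitted on 2013-2016 and projected to 2017-2018, and report it with its interval. The mid-points are 3 years apart (2014.5 and 2017.5), so a drift of +2 points per year would show as 6 points of VA share, or 0.3 injury points at an ATE of 5. A result near zero is reassuring only if the interval is narrow enough to exclude a drift of that order.
5. Attribute the excess to the cannula change only if these analyses agree.

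The cost is some SAP wording and a few extra runs on data already within the study. The extrapolated benchmark will have a wider interval, and the placebo will have limited precision.
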